5.2 Treatment Plan

5.2.1 Patients to take 200 mg PO twice daily until disease progression or toxicity. 28 days will be considered one cycle. Capsules will be swallowed unchewed with a glass of liquid of about one cup and with a dose interval of 12 hours. Patients will be instructed to take their medication at the same time every day, after food intake. If a patient misses a dose, the missed dose will not be made up. The patient should be instructed to take the next dose at the next scheduled time.

5.3 Criteria for removal from treatment

5.3.1 Inability to tolerate Nintedanib at the lowest doses because of toxicity.

5.3.2 Patients may choose to withdraw from the study at any time for any reason.

5.3.3 Patients with evidence of disease progression or significant side effects will be removed from study.

5.3.4 Patients who become pregnant will be removed from the study.

6.0 TREATMENT MODIFICATIONS

Study Drug	2 Level reduction	1 Level reduction	Initial dose level
Nintedanib	100 mg BID 1 100 mg capsule BID	150 mg BID 1 x 150 mg capsule BID	200 mg BID 2 x 100 mg capsules BID

Please note that this section is referring to the active version of the NCI Common Toxicity Criteria Version 4.0 grading.

6.1 Management of diarrhea

CTCAE v4.0 Grade	Action for Nintedanib and Anti-diarrheal treatment	Action for Nintedanib after recovery of diarrhea ¹
Grade 1	Continue Nintedanib No Anti-diarrheal treatment	No dose reduction of Nintedanib
Grade 2	Continue Nintedanib Anti-diarrheal treatment according to the local standard e.g., loperamide p.r.n.	No dose reduction of Nintedanib
Grade 2 \geq 7 days despite optimal medical management or Grade \geq 3 or any diarrhea independent of CTCAE grade leading to hospitalization of the patient		
First episode	TEMPORALLY Nintedanib until recovery ¹ AND Anti-diarrheal treatment according to the local standard e.g., loperamide p.r.n.	Reduce Nintedanib dose to 2 x 150 mg after recovery of diarrhea ¹
Second episode	TEMPORALLY STOP Nintedanib until recovery ¹ AND Anti-diarrheal treatment according to the local standard e.g., loperamide p.r.n.	Reduce Nintedanib dose to 2x 100 mg after recovery of diarrhea ¹
Third episode	PERMANENTLY discontinue Nintedanib treatment AND Anti-diarrheal treatment according to the local standard e.g., loperamide p.r.n.	PERMANENTLY discontinue Nintedanib treatment

¹Until resolution to less than or equal to the patient's pre-therapy status at study enrollment.

6.2 Management of liver enzyme elevations: If liver enzyme elevations are considered to be related to Nintedanib the following algorithm should be followed. This recommendation for the management of Nintedanib-induced liver toxicity is valid ONLY for patients with inclusion criteria: AST/ALT < 1.5 ULN and bilirubin ULN in

patients with no metastases in liver and, AST/ALT < 2.5 ULN and bilirubin \leq ULN in patients with metastases in liver.

ALT, AST and bilirubin elevation	1 st episode	2 nd episode	3 rd episode
ALT and/or AST \leq 5x ULN with bilirubin \leq 1.5 ULN	Continue Nintedanib, No dose reduction	Continue Nintedanib, No dose reduction	Continue Nintedanib, No dose reduction
ALT or AST > 2.5 ULN in conjunction with bilirubin > 1.5 ULN	TEMPORARILY STOP Nintedanib until recovery* Then reduce Nintedanib dose ¹	TEMPORARILY STOP Nintedanib until recovery* Then reduce Nintedanib dose ¹	PERMANENT discontinuation of Nintedanib treatment
ALT or AST > 5x ULN	TEMPORARILY STOP Nintedanib until recovery* Then reduce Nintedanib dose ¹	PERMANENT discontinuation of Nintedanib treatment	PERMANENT discontinuation of Nintedanib treatment
Bilirubin > 3.0 ULN	TEMPORARILY STOP Nintedanib until recovery* Then reduce Nintedanib dose ¹	PERMANENT discontinuation of Nintedanib treatment	PERMANENT discontinuation of Nintedanib treatment

*ALT and or AST \leq 2.5x ULN with bilirubin \leq 1.5 ULN or baseline at study enrollment.

¹Nintedanib dose reductions : from 200 mg bid to 150 mg bid and from 150 mg bid to 100 mg bid

Revised to change “ALT and/or AST \leq 2.5x ULN with bilirubin \leq 1.5 ULN” to “ALT and/or AST \leq 5x ULN with bilirubin \leq 1.5 ULN” in order to provide direction for participants with an “ALT and/or AST > 2.5 but \leq 5x ULN with bilirubin \leq 1.5 ULN”.

Revised from “*CTCAE v4.0, grade \leq 1 or baseline at study enrolment” to “*ALT and or AST \leq 2.5x ULN with bilirubin \leq 1.5 ULN or baseline at study enrollment.” Change was made due to variations regarding hepatic toxicity in CTCAE v3.0 and CTCAE v4.0. The Nintedanib modifications for hepatic toxicity were initially based on CTCAE v3.0. CTCAE v 3.0 defined grade 1 hepatic toxicity was defined as ALT and or AST \leq 2.5x ULN. However, CTCAE v 4.0 grade 1 hepatic toxicity is defined ALT and or AST \leq 3.0x ULN. Safety data up to date has used CTCAE v3.0. For safety considerations in prior studies in these series the criteria for return to baseline was ALT and/or AST \leq 2.5x ULN with bilirubin \leq 1.5 ULN or returning to baseline at study enrollment. To improve patient safety we will use these parameters rather than CTCAE v4.0 study criteria.

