6.3 Management of nausea and vomiting for trials investigating monotherapy of Nintedanib

In order to reduce the occurrence and the intensity of emesis the patients should be treated according to the following recommendations:

CTCAE v4.0 Grade	Antiemetic treatment	Dose of Nintedanib
Nausea =1	No antiemetic treatment	No dose reduction
Nausea 2 and/or vomiting =1	No Nintedanib treatment pause Antiemetic treatment according to local standard of care, e.g., metoclopramide or dimenhydrinate, or prochlorperazine If ineffective, patients should be treated according to treatment of vomiting ≥ 2 or nausea CTCAE Grade ≥ 3 .	No dose reduction
Vomiting ≥ 2 and/ or nausea ≥ 3		
First episode	Treatment with Nintedanib discontinued and resumed upon recovery ¹ Antiemetic treatment according to local standard of care e.g., with 5-HT ₃ receptor antagonist* and/or corticosteroid	Nintedanib: dose reduction ²
Second episode	Treatment with Nintedanib discontinued and resumed upon recovery ¹ Treatment as above	Nintedanib: dose reduction ²
Third episode	As above	Nintedanib: discontinuation

¹CTCAE grade ≤ 1 or baseline at study enrolment.

²Nintedanib dose reductions : from 200 mg bid to 150 mg bid and from 150 mg bid to 100 mg bid

* Note: Tropisetron and dolasetron should be avoided due to genetically polymorphic metabolism by CYP2D6.

THIS SPACE LEFT INTENTIONALLY BLANK

6.4 Management of non-hematologic adverse events other than emesis, liver enzyme elevations, and diarrhea

CTCAE v4.0 Grade 3 or 4	Nintedanib
First Episode	TEMPORARILY Stop Nintedanib treatment until recovery ¹ Then Nintedanib dose reduction ²
Second Episode	TEMPORARILY Stop Nintedanib treatment until recovery ¹ Then Nintedanib dose reduction ²
Third Episode	PERMANENT Nintedanib treatment discontinuation

¹Until resolution to less than or equal to the patient's pre-therapy value at study enrollment.

²Nintedanib dose reductions : from 200 mg bid to 150 mg bid and from 150 mg bid to 100 mg bid

6.5 Patients should PERMANENTLY discontinue treatment with Nintedanib in the event of:

- Intolerable Adverse Events (CTCAE v4.0 grade 3 or 4) that cannot be managed by dose reduction.
- Nausea or vomiting CTCAE v4.0 grade 2 for 5 or more consecutive days despite optimal supportive care and dose reduction of study medication.
- Diarrhea CTCAE v4.0 grade ≥ 2 for 8 or more consecutive days despite optimal supportive care and dose reduction of study medication.

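### The diarrhea table in section 6.1 fixes the restart dose by episode number, so a patient already reduced for another toxicity is told to reduce to the current dose or a higher one

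*Combined protocol and SAP*

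**What the plan says.** Section 6.0 sets three dose levels: 200 mg BID to start, then "150 mg BID 1 x 150 mg capsule BID", then 100 mg BID.

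Section 6.1 applies to grade 2 diarrhea lasting 7 days or more despite treatment, to grade 3 or worse, and to "any diarrhea independent of CTCAE grade leading to hospitalization of the patient". The drug is held until recovery. The restart dose is then set by episode number:

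- First episode: "Reduce Nintedanib dose to 2 x 150 mg after recovery of diarrhea".
- Second episode: "Reduce Nintedanib dose to 2x 100 mg after recovery of diarrhea".
- Third episode: permanent discontinuation.

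The tables in 6.2 (liver enzymes), 6.3 (nausea and vomiting) and 6.4 (other non-hematologic events) work differently. They call for a reduction, and a footnote defines it as 200 to 150 or 150 to 100 mg BID, so the step depends on the current dose. In 6.4 the trigger is "CTCAE v4.0 Grade 3 or 4" and the action after recovery is "Then Nintedanib dose reduction". Its heading leaves diarrhea out: "Management of non-hematologic adverse events other than emesis, liver enzyme elevations, and diarrhea".

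Section 6.5 lists reasons to stop permanently. One is diarrhea of grade 2 or worse "for 8 or more consecutive days despite optimal supportive care and dose reduction of study medication". Section 6.6 rules out any dose escalation or re-escalation.

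**The concern.** For a patient whose only toxicity is diarrhea, 6.1 is coherent: 200, 150, 100, stop. It goes wrong when a patient has already been reduced under another table. The instruction is to reduce, but the dose named may be the one already being taken, or a higher one.

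That route is clinically ordinary. Section 6.3 cuts the dose at a first episode of grade 2 vomiting, and section 4.1.9.1 lists vomiting and diarrhea among the most frequent adverse events.

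At stake is dosing consistency after severe or hospitalizing diarrhea. One site could act on the verb and go to 100 mg BID. Another could act on the number and restart at 150 mg BID. Neither would plainly be in breach of the text.

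**Working it through.** No figure in the plan has to be reproduced. The check crosses each possible current dose with the two dose cells of 6.1, then looks for a rule elsewhere that settles the conflict.

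**Reading of the numbers.** I read 2 x 150 mg as 150 mg twice daily, which matches the first reduction level in 6.0. Two 150 mg capsules per dose would be 300 mg BID, above the starting dose.

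**Episode counting.** I assume each table counts its own episodes. The text does not say so, but 6.2 supports it: ALT or AST above 5 times ULN stops treatment at the second episode, while the combined transaminase and bilirubin row stops it at the third. Pooling across toxicities would permanently stop a patient at a first transaminase event after a single diarrhea episode, which is implausible.

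**Named dose against current dose.**

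| Diarrhea episode | Current dose (BID) | Dose named in 6.1 (BID) | Effect |
|---|---|---|---|
| First | 200 mg | 150 mg | reduction |
| First | 150 mg | 150 mg | no change |
| First | 100 mg | 150 mg | increase, barred by 6.6 |
| Second | 150 mg | 100 mg | reduction |
| Second | 100 mg | 100 mg | no change |

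A second episode at 200 mg BID cannot arise, because the first would already have led to 150.

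**Order of events, if the named dose is followed.**

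- First diarrhea episode (6.1), then a first grade 3 or 4 event under 6.4: 200 → 150 → 100 mg BID, or 2 × 100 = 200 mg/day.
- The 6.4 event, then the first diarrhea episode: 200 → 150 → 150 mg BID, or 2 × 150 = 300 mg/day.

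**Rules that might settle it.**

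- 6.0 lists the levels but does not say how reductions for different toxicities combine.
- The 6.4 footnote cannot be borrowed, because its heading excludes diarrhea.
- 6.5, diarrhea bullet: this needs 8 or more days. A patient already reduced may be read as meeting it, so for grade 2 diarrhea the gap is essentially day 7. The gap that matters is grade 3 or worse, or hospitalizing, diarrhea lasting under 8 days.
- 6.5, first bullet: this covers grade 3 or 4 events that dose reduction cannot manage. At 150 mg BID a lower level is still available.
- 5.3.3 allows removal for significant side effects but names no dose.
- 6.6 blocks a move from 100 to 150 mg BID. It does not block restarting at 150 from 150.

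None of these names the restart dose.

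**The case against.** The best defense is that tying the restart dose to the diarrhea episode is a legitimate choice, that the verb makes the intent clear, and that the table fails only when two toxicity tables meet in one order. Part of this stands. Most patients never reach the conflict, and a careful investigator could infer 100 mg BID. But the cell prints 150, and no other section corrects it.

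The safeguards are real. The drug is held until recovery, a second episode goes to 100 mg BID, a third ends treatment, and 5.3.3 and the first bullet of 6.5 are partial backstops. They limit the harm without supplying the missing dose.

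A reader might also draw stronger conclusions that the documents do not support:

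- **That about 1 of 56 patients is affected.** Assume 10 to 30% are already at 150 mg BID. With the 8% ceiling for grade 3 gastrointestinal events (4.1.9.1), that gives 56 × 0.10 × 0.08 = 0.45 to 56 × 0.30 × 0.08 = 1.34. With the 16% seen at 250 mg BID in ovarian cancer (2.4), it gives 0.90 to 2.69. The 10 to 30% has no source. Both event rates cover all grade 3 gastrointestinal events, and the 16% comes from a higher dose. The product also assumes independence and places every diarrhea event after the other reduction. Fifty-six is a maximum: if accrual stops at 27, the 8% rate gives 0.22 to 0.65. In the other direction, low-grade hospitalizing diarrhea is not counted. Section 4.1.9.2 describes transaminase rises as rare in Caucasian patients at 150 or 200 mg BID, so the liver route to a prior reduction should be uncommon.
- **That restarting at 150 rather than 100 mg BID causes more recurrent diarrhea.** Section 2.4 reports no obvious rise in gastrointestinal events with dose up to 250 mg BID.
- **That the protocol directs a dose increase at 100 mg BID.** The cell points upward, but 6.6 forbids it. The footnotes in 6.2 to 6.4 name no step from 100 mg BID either, so the lack of guidance at the lowest level is not confined to 6.1.

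**Conclusion.** Wrong as written, minor. The fixed doses in 6.1 conflict with their own instruction to reduce when a patient is already at 150 mg BID for another toxicity, and at 100 mg BID the first-episode cell conflicts with 6.6. The size that can be stated from the text is a final dose of 200 or 300 mg/day for the same two first events, depending on their order, when the printed number is followed. This is a difference in dose, not a measured risk.

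The conclusion rests on episodes being counted per toxicity, which is inferred. Under pooled counting, a diarrhea episode in a patient reduced once before would count as the second and lead to 100 mg BID, so the conflict at 150 would disappear. The number of patients affected cannot be derived but is likely very small. The two-stage design's error rates and power do not change.

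**What to change.** In both the first- and second-episode cells of 6.1, replace the fixed dose with:

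> Reduce by one dose level from the current dose (200 to 150, 150 to 100 mg BID). If already at 100 mg BID, resume at 100 mg BID after recovery unless 5.3.1, 6.5 or the third-episode rule requires discontinuation. The dose is never raised (6.6).

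Leave the third-episode cell as it is.

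With this text, both orders of the two events above end at 100 mg BID. A patient whose only toxicity is diarrhea keeps the present sequence of 200, 150, 100, stop. A patient at 100 mg BID still has a stated restart dose and is not stopped automatically.

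The change takes two table cells in an amendment, with no added procedures or patients. The downside is slightly lower exposure in a few patients. Someone at 150 mg BID for another toxicity would restart at 100 after a first diarrhea episode, where following today's number would keep 150 until a second.

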 - o Any hormonal therapy directed at the malignant tumor must be discontinued at least one week prior to registration. Continuation of hormone replacement therapy is permitted.
 - Any other prior therapy directed at the malignant tumor, including immunologic agents, must be discontinued at least three weeks prior to registration. If the

prior therapy was with bevacizumab then at least 4 weeks after treatment discontinuation must have elapsed prior to treatment on this study.

- h) Prior therapy
 - Patients must have had one prior platinum-based chemotherapeutic regimen for management of primary disease containing carboplatin, cisplatin, or another organoplatinum compound. This initial treatment may have included intraperitoneal therapy, high-dose therapy, consolidation, non-cytotoxic agents or extended therapy administered after surgical or non-surgical assessment.
 - Patients are allowed to receive, but are not required to receive, two additional **cytotoxic regimens** (a total of 3 cytotoxic regimens) for management of recurrent or persistent disease according to the following definition:
 - Patients who have received only one prior cytotoxic regimen (platinum-based regimen for management of primary disease), must have a platinum-free interval of less than 12 months, or have progressed during platinum-based therapy, or have persistent disease after a platinum-based therapy. Patients must NOT have received any non-cytotoxic therapy for management of recurrent or persistent disease other than bevacizumab-containing regimens. Patients are allowed to receive, but are not required to receive, biologic (non-cytotoxic) therapy as part of their primary treatment regimen.
- i) Patients must have adequate:
 - Bone marrow function: Absolute neutrophil count (ANC) greater than or equal to 1,500/mcl, equivalent to NCI Common Toxicity Criteria version 4.0 (CTCAE v4.0) grade 1. Platelets greater than or equal to 100,000/mcl. Hemoglobin (Hb) greater than or equal to 9.0 g/dL.
 - Renal function: Creatinine less than or equal to 1.5 x institutional upper limit of normal (ULN), equivalent to the active version of the NCI AE grade 1.
 - Hepatic function: Bilirubin should be within normal limits (CTCAE v4.0, grade 1). ALT/AST, should be less than or equal to 1.5 x ULN (CTCAE v4.0 grade 1). For patients with liver metastases, ALT/AST should be less than or equal to 2.5 x ULN. Alkaline phosphatase should be less than or equal to 2.5 x ULN (CTCAE v4.0 grade 1).

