4.1.9.2 Hepatic adverse events: The predominant dose limiting toxicity in phase I dose escalation trials was reversible elevation of hepatic transaminases, more pronounced for ALT than for AST. At doses below 200 mg bid no CTCAE grade 3+4 increases have been observed. According to phase II data, the probability to suffer from liver enzyme elevations of CTCAE grade 3 or 4 within the first two months of Nintedanib treatment is 10-15% for patients treated with 250 mg bid of Nintedanib. An increase of transaminases was only rarely observed in Caucasian patients treated with 150 mg bid or 200 mg bid. An association with hyperbilirubinemia was rare, and was (if at all) represented by a low grade increase of bilirubin with only one exception in a patient with tumor stenosis of the ductus hepatocholedochus and grade 3 bilirubin increase two weeks after cessation of therapy. γ -GT elevations, either as isolated increases or in combination with transaminitis, were observed frequently. Enzyme elevations generally normalized upon dose reduction or discontinuation. No drug-related hepatic failure was reported [8].

The current dose of Nintedanib in all studies is limited to 200 mg bid and, all studies require monitoring of liver enzyme tests. In addition, all studies include specific dose reduction schemes regarding liver enzyme elevations [8].

4.1.9.3 Infection adverse events: Infections have been observed but were expected for advanced cancer populations and age group. Only a few were considered drug related.

4.1.9.4 Thromboembolic and cardiac adverse events: In the combined phase I and II monotherapy trials (1199.1-3, 1199.9, 1199.10, 1199.11, 1199.16, 1199.19), there were 13 patients (3.7%) with events from the “selected thrombotic events” category which included pulmonary embolism (3), deep vein thrombosis (2), myocardial infarction (2), transient ischemic attack (2), aphasia (1), hemiparesis (1), thrombophlebitis (1), and thrombosis (1). Five of these events (1.4%) were considered treatment

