- In the event that Nintedanib is withheld for > 21 consecutive days due to treatment-related toxicity, Nintedanib will be permanently discontinued.

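### Section 6.2: when a severe ALT/AST elevation with raised bilirubin recurs, one row of the liver table says resume at a reduced dose, another says stop permanently, and no rule says which governs

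*Combined protocol and SAP*

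**What the plan says.** Section 6.2 gives actions by episode for liver elevations that are considered related to nintedanib. Besides a row under which treatment simply continues (ALT and/or AST up to 5 × ULN with bilirubin up to 1.5 × ULN), there are three stop rows:

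| Row | Trigger | 1st episode | 2nd episode | 3rd episode |
|---|---|---|---|---|
| Combined | "ALT or AST > 2.5 ULN in conjunction with bilirubin > 1.5 ULN" | hold, then reduce | hold, then reduce | permanent stop |
| Transaminase | "ALT or AST > 5x ULN" | hold, then reduce | permanent stop | permanent stop |
| Bilirubin | "Bilirubin > 3.0 ULN" | hold, then reduce | permanent stop | permanent stop |

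The footnotes define recovery (ALT/AST at or below 2.5 × ULN with bilirubin at or below "1.5 ULN or baseline at study enrollment") and the dose steps, 200 to 150 to 100 mg bid. They do not say which row applies when several are met, or whether episodes are counted within a row or across rows.

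The general rules elsewhere are:
- Section 6.5: "In the event that Nintedanib is withheld for > 21 consecutive days due to treatment-related toxicity, Nintedanib will be permanently discontinued".
- Section 5.3.1 removes a patient for "Inability to tolerate Nintedanib at the lowest doses because of toxicity".
- Section 6.6 rules out re-escalation.

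**The concern.** The combined row has a floor on both measurements and a ceiling on neither. A patient with ALT 6 × ULN and bilirubin 2 × ULN therefore meets the combined row and the transaminase row at once. At a second such episode the first allows a restart and the second forbids it.

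The conflict also runs the wrong way clinically. A second isolated ALT/AST elevation above 5 × ULN must end treatment. The same elevation with raised bilirubin can be read as allowing rechallenge.

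Section 4.1.9.2 names transaminase elevation as the predominant dose-limiting toxicity in the phase I dose-escalation trials, and this is a multi-center study. Sites could treat the same recurrent injury differently and each be following the table. What is at stake is consistent and safe dosing, not the efficacy inference.

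**Working it through.** **Inputs.** All come from the Section 6.2 table. The cut-offs are ALT/AST 2.5 and 5 × ULN and bilirubin 1.5 and 3.0 × ULN. I take the higher of ALT and AST to set the band.

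**Step 1: rows met in each cell.**

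| ALT/AST | Bilirubin ≤ 1.5 | Bilirubin > 1.5 to 3.0 | Bilirubin > 3.0 |
|---|---|---|---|
| ≤ 2.5 | continue | no row | bilirubin |
| > 2.5 to 5 | continue | combined | combined + bilirubin |
| > 5 | transaminase | combined + transaminase | all three stop rows |

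Five cells meet exactly one row, three meet more than one, and one meets none (5 + 3 + 1 = 9). Six cells meet at least one stop row.

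**Step 2: the same overlapping cell recurs.** Every row met is then at its second episode, whether episodes are counted per row or pooled. The combined row says hold and reduce, and the stricter row or rows say permanent stop. This is a conflict in 3 of 3 overlapping cells under either counting rule. At the first episode the rows agree.

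**Step 3: all ordered pairs of stop-row episodes.** There are 6 × 6 = 36 pairs. At a second episode the combined row always says hold and reduce, so a conflict needs a second episode in an overlapping cell with a stricter row already at its second count.
- Pooled counting: 3 overlapping cells × 6 possible first cells = 18 of 36.
- Per-row counting: the first episode must have met the same stricter row.
  - Second cell ALT/AST > 2.5 to 5 with bilirubin > 3.0: 3 first cells have bilirubin > 3.0.
  - Second cell ALT/AST > 5 with bilirubin > 1.5 to 3.0: 3 first cells have ALT/AST > 5.
  - Second cell ALT/AST > 5 with bilirubin > 3.0: 3 + 3 − 1 = 5 first cells have either.
  - Total: 3 + 3 + 5 = 11 of 36.

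Per-row counting can also produce a conflict at a third combined-row episode that is the first above 5 × ULN. The combined row then says permanent stop and the transaminase row says reduce.

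**Step 4: effect of a precedence sentence.** The actions are ordered: permanent stop is stricter than hold and reduce. Taking the strictest leaves one action in every case, so 0 of 36 pairs conflict under either counting rule. The third-episode case is settled as well.

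**Step 5: other sections.**
- Section 6.4 excludes liver enzyme elevations by its title and acts only at grade 3 or 4.
- Sections 5.3.1, 5.3.3 and 6.5 are general stopping rules.
- Section 10.4 sets a reporting timeline and gives no dosing instruction.

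None of these ranks the rows of Section 6.2.

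**The case against.** The strongest reply is that this hardly ever matters and that a careful investigator would stop anyway. Much of that stands. A first stop-row episode forces a reduction, so a second one occurs at 150 mg bid or lower. Section 4.1.9.2 reports: "At doses below 200 mg bid no CTCAE grade 3+4 increases have been observed". It also calls an association with hyperbilirubinemia rare. Restart needs recovery, and a toxicity hold beyond 21 days ends treatment. Section 6.2 describes itself as a recommendation and leaves attribution to the investigator. This limits the frequency and the harm. It does not tell two sites which row to follow.

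A reader might infer three stronger points, which the documents do not support.

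- **That episodes must be pooled across rows.** Five of the six stop cells have ALT/AST > 5 or bilirubin > 3.0 × ULN, giving 5 × 6 = 30 pairs with such a second episode. With the strictest row governing and per-row counting, 13 of the 30 still resume. But those 13 are the table's own first-episode instruction for that row. Nothing in the protocol says that they should stop. Pooling is the more cautious option, but it tightens dosing policy and is not needed to remove the contradiction.
- **That the empty cell is a safety hole of equal weight.** Bilirubin above 1.5 to 3.0 × ULN with ALT/AST raised but at or below 2.5 × ULN meets no row. A bilirubin rise alone could put a patient there, since Section 3.1 says "For patients with liver metastases, ALT/AST should be less than or equal to 2.5 x ULN". Yet the cell lies below every stop trigger, and the default under Section 5.2.1 is to continue until progression or toxicity. Section 10.4 items (i) and (ii) do not reach it, but item (iii), on repeat elevated results within 2 weeks, may. It needs clarifying and no more.
- **That 18 or 11 of 36 is a risk.** These are combinations of cells with equal weight, not patient probabilities.

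**Conclusion.** The table contradicts itself. In 3 of 9 cells a recurrence is told both to resume at a reduced dose and to stop permanently, whichever way episodes are counted, and no precedence is stated. This is more than missing detail, because one of the two stated instructions can permit rechallenge after the more severe combined injury. It should be corrected.

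The practical size is small: maximum accrual is 56, and the conflict needs a second related episode with both ALT/AST and bilirubin raised, on a reduced dose. That judgment rests on the experience reported in Section 4.1.9.2 carrying over to this population, and on episodes in the continue row not being counted, since they force no reduction. The documents give no rate for recurrent combined elevations, so I put no number on the patients affected.

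The 6-month PFS analysis and its error rates are unaffected, because stopping drug is not a PFS event under Section 8.1.6 or 11.3.

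**What to change.** Add under the Section 6.2 table: *If more than one row applies, the strictest action governs.* This alone takes the conflicts from 18 or 11 of 36 pairs to 0.

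Capping the combined row at ALT/AST 5 × ULN and bilirubin 3.0 × ULN is an alternative. It gives 0 of 36 with pooled counting but leaves 4 of 36 with per-row counting, where the transaminase and bilirubin rows disagree, so the precedence sentence is the simpler repair.

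Two further clarifications are for the sponsor-investigator:
- State whether episodes are counted per row or across the three stop rows. If pooled counting is chosen, present it as a policy decision.
- State the action, which may simply be to continue, for bilirubin above 1.5 to 3.0 × ULN with ALT/AST raised but at or below 2.5 × ULN.

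The cost is a short amendment of the kind already recorded beneath this table, with no extra tests or patients. The downside is that a few patients may stop drug at a second episode instead of resuming at a reduced dose.
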